8.4. Other Safety Analyses

The analyses of non-laboratory safety test results including ECGs and vital signs will be based on GSK Core Data Standards, unless otherwise specified. The details of the planned displays are presented in [Appendix 10: List of Data Displays](#).

ECG findings (Normal, Abnormal - not clinically significant, Abnormal – clinically significant) will be summarized by treatment group (and total for GTC1, GTC2 and GTC3) for each visit.

Raw value and change from baseline for vital sign data will be summarized by treatment group (and total for GTC1, GTC2 and GTC3) for each visit.

Any other safety endpoint will not be described in this RAP.

8.5. Study Specific Safety Analyses

Since urinary events are of interest for this study, some study specific safety analyses will be analysed for following item.

These analyses will be done by treatment group in only TC1, and using Safety population (SPDB).

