### **Safety**

All AEs that occur during the study will be recorded and classified using the current Medical Dictionary for Regulatory Activities (MedDRA). Events will be summarized overall, by treatment cycle and for the first 12 week of 1st treatment phase (adverse event that occurs  $\leq 84$  days from 1st treatment). Frequencies of AEs will be presented by system organ class and preferred term. Summaries of treatment-related AEs (study drug-related, injection procedure related), AEs leading to discontinuation, AEs by intensity, and SAEs also will be provided.

PVR urine volume will be summarized by visit and etiology. The proportion of patients who will have a change from baseline in PVR category (urine volume of  $< 100$  mL,  $\geq 100$  to  $< 200$  mL,  $\geq 200$  to  $< 350$  mL, and  $\geq 350$  mL) will be summarized by visit and etiology.

The observed value of clinical laboratory test and its change from baseline will be summarized by treatment group. The number of subjects with values outside of normal range by visit will be tabulated by treatment group to evaluate the changes in clinical laboratory tests.

The observed value of vital signs and changes from baseline will be summarized by treatment group. Also the ECG findings by visit will be summarized by treatment group.

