2. SUMMARY OF KEY PROTOCOL INFORMATION

2.1. Changes to the Protocol Defined Statistical Analysis Plan

Changes from the originally planned statistical analysis specified in the protocol are outlined in [Table 1](#).

Table 1 Changes to Protocol Defined Analysis Plan

Protocol	Reporting & Analysis Plan	
Statistical Analysis Plan	Statistical Analysis Plan	Rationale for Changes

To use MMRM and ANCOVA for percent change from baseline in
 
 • Daily average number of urinary incontinence • Average volume voided per void • Daily average number of voids 	
To provide only summary statistics, not statistical analyses.
	
Upon blind review for endpoints of percent change from baseline, it was considered that normality assumptions are violated for percent change from baseline in "Daily average number of urinary incontinence". Therefore, it is not appropriate to apply MMRM/ANCOVA for these endpoints and only summary statistics will be provided. To be consist with this change, only summary statistics of percent change from baseline in "Average volume voided per void" and "Daily average number of voids" will be provided without any statistical analyses.

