6.1.3. Demographic and Baseline Characteristics

Each of the following types of data will be summarized in each treatment group and total:

- Demographic data (age, sex, ethnicity, weight, height, body mass index (BMI), race and racial combinations)

- Baseline disease characteristics
 - Items of diary data
 - ✧ Daily average episodes of urinary incontinence
 - ✧ Daily average episodes of voids
 - ✧ Average volume voided per void
 - PVR volume and number and percentage of subjects with its category (no measurement of PVR, < 100 mL, >= 100 mL to < 200 mL, >= 200 mL to < 350 mL or >= 350mL)
 - Duration of NDO history
 - Number and percentage of subjects with NDO etiology (SCI with neurological injury level C5 to C8, SCI with neurological injury level T1 or below, or MS)
 - (For subject with SCI only): Number and percentage of subjects with ASIA (American Spinal Injury Association) impairment scale (A: complete, B: sensory incomplete, C: motor incomplete, D: motor incompletes or E: normal)
 - Number and percentage of subjects of void pattern (CIC only, Mixed (catheterization and spontaneous void), Spontaneous void only, Mixed (Intermittent balloon catheter and spontaneous void), CIC and Intermittent balloon catheter or Mixed (CIC, Intermittent balloon catheter and spontaneous void))
 - Urodynamics
 - ✧ Maximum cystometric capacity (MCC)
 - ✧ Maximum detrusor pressure during the first involuntary detrusor contraction (IDC) ($P_{\max IDC}$)
 - ✧ Volume at first involuntary detrusor contraction ($V_{P_{\max IDC}}$)
 - ✧ Maximum detrusor pressure during the storage phase ($P_{\det Max}$)
- Age ranges (for EudraCT requirement)

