8. SAFETY ANALYSES

The safety analyses will be based on the “Safety” population, unless otherwise specified. In detail, each Safety population will be used for each study phase as below table. In principle, summaries for TC1 will be only by treatment group, and summaries for GTC1, GTC2, GTC3 and Overall will be by treatment group and its total.

For AEs:

Study phase	Population	Summary Group
TC1	SPDB	By treatment group
GTC1	SP1	By treatment group and total
GTC2	SP2	By treatment group and total
GTC3	SP3	By treatment group and total
Overall	SP1	By treatment group and total

NOTES:

- The definition of population is described in [Analysis Populations](#).

For other than AEs:

Study phase	Population	Summary Group
TC1	SPDB	By treatment group
GTC1, GTC2, GTC3	SP1	By treatment group and total

NOTES:

- The definition of population is described in [Analysis Populations](#).

Safety data from unscheduled visit will not be included in safety analysis (but included in listing), and the safety data at last visit will be treated as Study Exit in safety analyses (but treated as Withdrawal in listing).

Visit displayed in safety analyses will be summarized below table for study phases and endpoints. SPDB (for TC1) and SP1 (for GTC1, GTC2 and GTC3) will be used for these summaries. Separate displays will be provided for TC1 and for GTCs (GTC1, GTC2 and GTC3).

Endpoints	Study phase	Study visit displayed in safety analyses table
Vital Sign	TC1	Baseline, Week 2, Week 6, Week 12, Week 24, Week 36, Study exit
	GTC1	Study baseline, Qualification for GTC1[1], Week 0 [1], Week 2, Week 6, Week 12, Week 24, Week 36, Study exit
	GTC2	Qualification for GTC2, Week 0, Week 2, Week 6, Week 12, Week 24, Study exit
	GTC3	Qualification for GTC3, Week 0, Week 2, Week 6, Week 12, Study exit
Clinical laboratory (chemistry and hematology), ECG	TC1	Baseline, Week 12, Study exit
	GTC1	Study baseline, Qualification for GTC1 [1], Week 12, Study exit

Endpoints	Study phase	Study visit displayed in safety analyses table
	GTC2	Qualification for GTC2, Week 12, Study exit
	GTC3	Qualification for GTC3, Week 12, Study exit
Body Weight	TC1	Baseline, Study exit
	GTC1	Study baseline, Qualification for GTC1 [1], Study exit
	GTC2	Qualification for GTC2, Study exit
	GTC3	Qualification for GTC3, Study exit
PVR	TC1	Baseline, Week 2, Week 6, Week 12, Week 24, Week 36, Study exit
	GTC1	Study baseline, Qualification for GTC1 [1], Week 2, Week 6, Week 12, Week 24, Week 36, Study exit

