	GTC2	Qualification for GTC2, Week 2, Week 6, Week 12, Week 24, Study exit
	GTC3	Qualification for GTC3, Week 2, Week 6, Week 12, Study exit

NOTES:

- Baseline means study baseline defined as [5.2](#).
- Study baseline will be used for the derivation of change from baseline
- Urinalysis results will be displayed by using worst case results post-baseline relative to baseline for protein and occult blood urinalysis only in accordance with IDSL standards rationale, not by visit
- Study exit includes withdrawal.
- [1]: only for subjects with Placebo at TC 1

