3.90.	SP1	LB3	Summary of Shift from Baseline with Relative to Normal Range in Hematology: GTCs	ICH E3		Y
Laboratory: Urinalysis						
3.91.	SPDB	UR1	Summary of Worst Case Urinalysis Results (Discrete or Character Values) Post-Baseline Relative to Baseline: TC1	ICH E3	Y	Y
3.92.	SP1	UR1	Summary of Worst Case Urinalysis Results (Discrete or Character Values) Post-Baseline Relative to Baseline: GTCs	ICH E3		Y
Laboratory: Hepatobiliary (Liver)						
3.93.	SP1	LIVER10	Summary of Hepatobiliary Laboratory Abnormalities	IDSL	Y	Y
ECG						
3.94.	SPDB	EG1	Summary of ECG Findings: TC1	IDSL	Y	Y
3.95.	SP1	EG1	Summary of ECG Findings: GTCs	IDSL		Y
Vital Signs						
3.96.	SPDB	VS1	Summary of Vital Signs Data by Visit: TC1		Y	Y
3.97.	SP1	VS1	Summary of Vital Signs Data by Visit: GTCs			Y

CONFIDENTIAL

204948

Safety : Tables						
No.	Population	IDSL / TST ID / Example Shell	Title	Programming Notes	Report at Interim	Report at Final
3.98.	SPDB	VS1	Summary of Change from Baseline in Vital Signs by Visit: TC1	ICH E3	Y	Y
3.99.	SP1	VS1	Summary of Change from Baseline in Vital Signs by Visit: GTCs	ICH E3		Y
Post Void Residual (PVR) urine volume						
3.100.	SPDB	Study specific	Summary of PVR urine volume:TC1		Y	Y
3.101.	SPDB	Study specific	Summary of Change from Baseline in PVR urine volume:TC1		Y	Y

CONFIDENTIAL

204948

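### Post-void residual volume has no planned summary after re-treatment, although SAP section 8 provides for one, and the protocol's PVR-category analysis is dropped undeclared

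*SAP*

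**What the plan says.** - **SAP section 8** gives, for each safety parameter, the visits to be displayed in TC1 (population SPDB) and in GTC1, GTC2 and GTC3 (population SP1). It states: "Separate displays will be provided for TC1 and for GTCs (GTC1, GTC2 and GTC3"). PVR has its own rows for all four phases; the GTC2 row reads "Qualification for GTC2, Week 2, Week 6, Week 12, Week 24, Study exit".
- **SAP 8.5**, the parent section of the PVR plan in 8.5.1, states: "These analyses will be done by treatment group in only TC1, and using Safety population (SPDB"). Section 8.5.1 plans summary statistics and a listing of PVR volume and its change, and no category table.
- **SAP 11.10.8** has two PVR tables: 3.100, titled "Summary of PVR urine volume:TC1", and 3.101, the matching change from baseline. Vital signs, by contrast, have entries such as "Summary of Change from Baseline in Vital Signs by Visit: GTCs".
- **Protocol 9.4.2 (Safety)** plans PVR volume by visit and etiology. It adds a second analysis: "The proportion of patients who will have a change from baseline in PVR category", with classes below 100, 100 to below 200, 200 to below 350, and 350 mL or more.
- **SAP 6.1.3** keeps those classes for baseline only: "PVR volume and number and percentage of subjects with its category".
- **SAP 2.1** says "Changes from the originally planned statistical analysis specified in the protocol are outlined in" its Table 1. That table has one row, on percent change in the diary endpoints. PVR is not mentioned.

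**The concern.** The SAP gives two incompatible scopes for the same parameter, and the narrower one reaches the table list. PVR is a listed parameter under the safety objectives in SAP 2.2, one of which concerns repeated dosing, and the schedule collects it after each re-treatment. For subjects randomised to placebo, the first re-treatment is their first exposure to active drug, and none of the PVR data from it would be summarised.

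The parameter is not incidental. Protocol 4.6.1 reports urinary retention after first treatment in 17.2% of patients on 200 U and 2.9% on placebo in the integrated earlier studies. Protocol 7.4.7 uses 200 and 350 mL as the boundaries for follow-up, and these are two of the three cut-points in the lost category table.

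The second issue is traceability. A protocol-specified analysis has disappeared, and the place where the SAP says departures are recorded does not record it.

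**Working it through.** No sample-size or power figure is involved. The check compares the section 8 visit table with the table list and counts rows.

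**Step 1. Visit table against table list (SAP 8 and 11.10.8).**

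| Parameter with by-visit rows in section 8 | GTC rows in section 8 | TC1 tables | GTC tables |
|---|---|---|---|
| Chemistry | yes | 3.79, 3.81, 3.83 | 3.80, 3.82, 3.84 |
| Hematology | yes | 3.85, 3.87, 3.89 | 3.86, 3.88, 3.90 |
| ECG | yes | 3.94 | 3.95 |
| Vital signs | yes | 3.96, 3.98 | 3.97, 3.99 |
| PVR | yes | 3.100, 3.101 | none |
| Body weight | yes | none named | none named |

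GTC tables for the first four parameters: 3 + 3 + 1 + 2 = 9. For PVR: 0. Urinalysis, handled as worst case rather than by visit, also has a GTC table (3.92). PVR is the only parameter with TC1 tables and no GTC tables, so this is not a general decision to stop at TC1. SAP 11.10.1 ends the safety table numbering at 3.101, so no later PVR table is missing from the list.

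**Step 2. Post-injection PVR rows in section 8.**

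- GTC1: weeks 2, 6, 12, 24, 36 and exit = 6
- GTC2: weeks 2, 6, 12, 24 and exit = 5
- GTC3: weeks 2, 6, 12 and exit = 4
- Total: 6 + 5 + 4 = 15

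**Step 3. Rows that reach no table.**

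- *Active drug first.* SAP 11.6.2 makes GTC1 the same days as TC1, so its 6 rows are covered by 3.100 and 3.101. Uncovered: 15 − 6 = 9.
- *Placebo first.* SAP 11.4.1.2 makes GTC3 not applicable, and GTC1 starts at the second treatment. Uncovered: 6 + 5 = 11.

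These are display rows, not observations. Two of the 11 cannot be separate visits. Re-treatment is not allowed before week 12, so week 36 of GTC1 falls at 12 + 36 = 48 weeks at the earliest. A second re-treatment is not possible before week 24, so week 24 of GTC2 falls at 24 + 24 = 48 weeks at the earliest. Both can only be the exit visit, placed in that row under SAP 11.3.2. Counting distinct scheduled visits gives 11 − 2 = 9.

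**Step 4. The category analysis.** Protocol 9.4.2 plans one; SAP 8.5.1 and 11.10.8 contain none; SAP Table 1 has no PVR entry. Other reductions are explained: SAP 5.4.1 gives small numbers as the reason for dropping the etiology split, and 8.5.2 gives fewer than 5 subjects as the reason for listing catheterization data only. No reason is given for PVR category.

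**Step 5. What is still reported.** Urinary retention and residual urine volume increased are adverse events of special interest (SAP 11.6.4). They are tabulated for GTC1, GTC2, GTC3 and overall in Tables 3.60, 3.63, 3.66 and 3.68. The gap is therefore PVR volume and category, not the rate of these events.

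**The case against.** The strongest reply is that the documents already settle the matter. The SAP's population section points to Appendix 10 for the displays. Appendix 10 agrees with 8.5, and 8.5 is the more specific text. Sections 8.3 and 8.4 name the GTCs where they are wanted. On this view the PVR rows in section 8 are leftovers, as the body-weight rows may be, and no programmer would be misled. That is a fair reading of which text governs. It also confirms the gap, because the governing list yields no PVR summary after re-treatment.

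Second, protocol 9.4.2 asks for adverse events by treatment cycle but for PVR only by visit and etiology. The per-cycle PVR displays therefore come from SAP section 8, not from an explicit protocol promise. This is correct. It does not help the category analysis, which the protocol does promise.

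Third, the adverse event tables may carry most of the clinical signal. For subjects not catheterizing at baseline, protocol 7.4.7 makes a PVR of 350 mL or more a retention event, and likewise 200 to below 350 mL with symptoms judged to need catheterization. This stands for those subjects. For mixed-pattern subjects, retention is recorded only on progression to exclusive catheterization, and residual urine volume increased depends on the investigator's judgement. A large rise in a mixed voider could therefore appear in neither.

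Fourth, the tables would be sparse. SAP 8.5.2 counts fewer than 5 subjects with the two void patterns it considers, and the number with other mixed patterns is not given. This stands. It applies equally to the TC1 PVR tables, which were kept.

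Finally, Listing 35 names no cycle, uses the same population as the all-cycle adverse event listings and is run again at the final analysis, so it may show later values. Read literally, though, 8.5 limits it to TC1.

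**Conclusion.** The concern holds. SAP section 8 conflicts with 8.5 and 11.10.8. As the table list stands, PVR is summarised in two tables for TC1 and none for the GTCs. In section 8's terms, 9 post-injection rows for active-first subjects and 11 for placebo-first subjects go unsummarised; the 11 represent 9 distinct scheduled visits. The protocol's change-in-category analysis is also missing, with no declaration and no stated reason.

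This should be corrected, but it does not affect the primary analysis or the tabulated rate of retention events. The conclusion assumes that Appendix 10 is the complete list of displays and that the separate mock-shell document adds none. The number of subjects affected cannot be worked out from the documents.

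**What to change.** 1. Add two tables on SP1, PVR value and change from baseline by visit, for GTC1, GTC2 and GTC3. Restrict them to the spontaneous and mixed void patterns defined in SAP 8.5.1.
2. Restore the protocol's table of change in PVR category by visit, using the four volume classes that SAP 6.1.3 already applies at baseline.
3. Amend 8.5 and 11.10.8 to match section 8, and add one sentence saying that Listing 35 covers all cycles.

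If TC1 only is intended, delete the GTC rows for PVR from section 8, declare both departures in SAP Table 1 with a reason, and confirm that Listing 35 covers all cycles. This is weaker, because the repeat-dose objective would still name PVR while providing no summary of it.

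The cost is two GTC tables and one category table at the final analysis (two category tables if split into TC1 and GTC parts), all from data already collected. Denominators will be small, so the tables should be presented as descriptive only.

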8.5.1. Post Void Residual (PVR) Urine Volume

PVR will only be measured in non-catheterizing subjects, or those with “mixed” patterns (ie, they do both CIC and spontaneous voiding). Therefore, analyses for PVR will include only subjects with Mixed (catheterization and spontaneous void), Spontaneous void only, Mixed (Intermittent balloon catheter and spontaneous void) or Mixed (CIC, Intermittent balloon catheter and spontaneous void)

Summary statistics and listing will be provided for PVR urine volume and its change from baseline.

Listing of PVR data will be produced. This listing will include the following items.

- Site ID, Subject ID, Treatment group, Visit, Date, Study day, PVR value, Change from baseline in PVR, Flag at initiating CIC

Flag at initiating CIC will be marked ONLY for subjects with “Spontaneous void only” or “Intermittent balloon catheter and spontaneous void” as void pattern. This flag will set to PVR data at the time of initiation of CIC (with the reason for urinary retention or elevated PVR) or 2 weeks prior to CIC if not available at the time of initiation.

Note that use of CIC includes use of indwelling catheter, if exists. The reason to use CIC are urinary retention, elevated PVR or other. Only data of use of CIC with the reason for urinary retention or elevated PVR will be used for any analyses.

8.5.2. Clean Intermittent Catheterization (CIC)

No summary table will be prepared for CIC related endpoints. In this study, CIC related endpoints for subjects with “Spontaneous void only” or “Intermittent balloon catheter and spontaneous void” as void pattern are of interest, but the number of subjects with “Spontaneous void only” or “Intermittent balloon catheter and spontaneous void” as void pattern are small (less than 5 in total). Therefore, only listing will be produced for CIC related endpoints.

Duration of using CIC in each CIC use will be listed. Duration of using CIC will be calculated for the CIC with the reason for urinary retention or elevated PVR not include CIC with reason for “other”. Duration of using CIC is calculated cumulatively as

$$(Duration\ of\ using\ CIC) = (Date\ of\ A) - (“start\ date\ of\ CIC”) + 1$$

- (For CIC not using at date of study complete or withdrawal) *Date of A* = “stop date of CIC”
- (For CIC using at date of study complete or withdrawal) *Date of A* = (later of “stop date of CIC” or “date of study complete or withdrawal”)

Time to onset of first CIC will be calculated as:

$$(Time\ to\ onset\ of\ first\ CIC) = (The\ date\ of\ using\ CIC\ first\ in\ TC1) - (the\ date\ of\ first\ treatment) + 1$$

Listing of CIC data will be produced. This listing will include the following items.

- Site ID, Subject ID, Treatment group, Start date of CIC / End date of CIC, Duration of CIC, Time to onset of first CIC in TC1, Reason for catheterization (urinary retention, elevated PVR or other), Additional reason for other

8.5.3. Ultrasound

The listing of kidney and bladder ultrasound data will be prepared.

Listing will display the date of morphology, Yes / No for “Was the subject detected kidney stone?” and Yes / No for “Was the subject detected bladder stone?” at least.

8.5.4. General Anesthesia

The listing of using general anesthesia will be prepared.

8.6. Patient Profile Listings

Listing for patient profiles will be produced if one of the events is reported below.

CV EVENTS (ARRHYTHMIAS, CONGESTIVE HEART FAILURE, CEREBROVASCULAR EVENTS STROKE AND TRANSIENT ISCHEMIC ATTACK, DEEP VEIN THROMBOSIS (DVT) /PULMONARY EMBOLISM (PE), MYOCARDIAL INFARCTION, PERIPHERAL ARTERIAL THROMBOEMBOLISM, PULMONARY HYPERTENSION, REVASCULARISATION, VALVULOPATHY) and DEATH

9. OTHER ANALYSIS

Any analyses of neutralizing antibody measurement will not be described in this RAP.

11. APPENDICES

11.1. Appendix 1: Protocol Deviation Management and Definitions for Per Protocol Population

11.1.1. Exclusions from Per Protocol Population

Per protocol population is not defined in this study.

CONFIDENTIAL

204948

11.2. Appendix 2: Schedule of Activities

11.2.1. Protocol Defined Schedule of Events

Table 2 Time and Events Table (Screening to Treatment phase 1)

	Screening	Treatment phase 1										
		All subjects				If subject was not re-treated						
Week (After 1st treatment)	Within 28 days	0	2	6	12	18 ^a (verification by tel.)	24	30 ^a (verification by tel.)	36	42 (verification by tel.)	48 (Study exit)	Withdrawal
Window			± 3 d	± 7 d	± 7 d	± 7 d	± 7 d	± 7 d	± 7 d	± 7 d	± 7 d	
Patient characteristics etc.												
Informed consent	X											
Medical history / demographics	X	X ^b										
Inclusion / exclusion criteria	X	X ^b										
Neutralizing antibody	X ^m										X	X
Efficacy												
Urodynamic assessment	X ^c			X								
Check of bladder diary ^d		X ^b	X	X	X	X	X	X	X	X	X	X
KHQ		X ^b		X	X		X		X		X	X
TBS			X	X	X		X		X		X	X
Safety												
Adverse events ^e		X	X	X	X	X	X	X	X	X	X	X
Physical exam	X										X	X
Height, Weight	X										X ^f	X ^f
Vital signs	X	X ^b	X	X	X		X		X		X	X
ECG	X				X						X	X
Clinical laboratory (hematology and blood chemistry)	X				X						X	X
HBsAg • HCVAb (for subjects who receive or plan to receive immunosuppressants)	X											
Urinalysis (dipstick)	X	X ^b	X	X	X		X		X		X	X
Urinalysis (clinical laboratory) / Urine culture / sensitivity ^g	X	X ^b	X	X	X		X		X		X	X
PVR	X ^c		X	X	X		X		X		X	X

CONFIDENTIAL

204948

Ultrasound (kidney / bladder)	X				X						X	X
Urine cytology	X											
PSA (Only male)	X											
Urinary pregnancy test (Only females of reproductive potential) ^h	X	X ^b	X	X	X		X		X		X	X
EDSS (Only MS patients)	X											
Investigational product												
Treatment of antibiotic ⁱ		X										
Treatment of investigational product		X										
Confirmation of qualification for re-treatment criteria ^{j, k}					X	X	X	X	X			
Concomitant meds / therapies	X ^l	X	X	X	X	X	X	X	X	X	X	X

d = day (s)

- (a) Patient can request re-treatment at any time via telephone since week 12 after 1st treatment. If the patient requests re-treatment via telephone, a qualification for re-treatment visit should be conducted within approximately 1-2 weeks of the patient request.
- (b) Performed prior to treatment.
- (c) May be performed during the screening period through Day 1 (prior to randomization) excluding diary data collection days
- (d) Diary must have been completed for any 3 consecutive days in the week prior to the visit (for screening phase only, it could have been completed for 3 consecutive days at any time during the screening phase). The volume voided is recorded by subjects for one 24-hour period during the 3 day diary collection period.
- (e) Only serious adverse events assessed as related to study participation or a GSK product will be recorded from the time when a subject consents
- (f) Measured only body weight
- (g) Urine culture and sensitivity is performed by the central laboratory when dipstick results are positive for nitrites or leukocyte esterase.
- (h) For patients with doubtful reaction in urinary pregnancy test, the investigator (or subinvestigator) may conduct serum pregnancy test.
- (i) For patients without a UTI as determined from the urinalysis or urine culture and/or investigator opinion, prophylactic antibiotic are to be administered 1 to 3 days before study treatment, on the day of treatment, and 1 to 3 days after treatment. For patients with a UTI as determined from the urinalysis or urine culture and/or investigator opinion, an antibiotic to which the identified organism is sensitive is to be administered at least 5 days prior to study treatment and continued for at least 3 days following the procedure.
- (j) If qualification for re-treatment criteria was met, the patient will undergo the exams specified in Table 2, column marked "If qualification for re-treatment criteria was met".
- (k) Patients who are not re-treated will remain in Treatment phase 1 and continue to visit at the scheduled study visit.
- (l) Patients who are using the medications or therapies urinary incontinence due to NDO should maintain the same dose from at least 7 days before the start of the screening phase throughout Treatment phase 1.
- (m) Samples may be collected during the screening period through Day 1 (prior to randomization)

CONFIDENTIAL

204948

Table 3 Time and Events Table [Treatment phase 1 (if qualification for re-treatment criteria was met) to treatment phase 2]

Week	Treatment phase 1	Treatment phase 2															
	If qualification for re-treatment criteria was met (Within 21 days prior to re-treatment)	1st re-treatment	Re-treatment (1st)							2nd re-treatment	Re-treatment (2nd)					Withdrawal	
			2	6	12	18 ^a (verification by tel.) _b	24 ^a	30 ^a (verification by tel.)	Study exit (48 weeks after 1st treatment)		2	6	12 ^a	18 ^a (verification by tel.)	Study exit (48 weeks after 1st treatment)		
Window		0	± 3 d	± 7 d	± 7 d	± 7 d	± 7 d	± 7 d	± 7 d	± 7 d	0	± 3 d	± 7 d	± 7 d	± 7 d	± 7 d	
Patient characteristics etc.																	
Neutralizing antibody									X							X	X
Efficacy																	
Check of bladder diary ^c	X		X	X	X	X	X	X	X	X		X	X	X	X	X	X
KHQ	X		X	X	X	X	X	X	X	X		X	X	X	X	X	X
TBS	X		X	X	X	X	X	X	X	X		X	X	X	X	X	X
Safety																	
Adverse events	X	X	X	X	X	X	X	X	X	X	X	X	X	X	X	X	X
Physical exam	X								X	X						X	X
Height, Weight	X ^d								X ^d	X ^d						X ^d	X ^d
Vital signs	X	X ^e	X	X	X			X	X	X	X ^e	X	X	X		X	X
ECG	X ^f				X				X	X ^f				X		X	X
Clinical laboratory (hematology and blood chemistry)	X				X				X	X				X		X	X
Urinalysis (dipstick)	X	X ^e	X	X	X			X	X	X	X ^e	X	X	X		X	X
Urinalysis (clinical laboratory) / Urine culture / sensitivity ^g	X	X ^e	X	X	X			X	X	X	X ^e	X	X	X		X	X
PVR	X		X	X	X			X	X	X		X	X	X		X	X
Ultrasound (kidney/bladder)	X ^f				X				X	X ^f				X		X	X
Urinary pregnancy test (Only females of reproductive potential) ^h	X	X ^e	X	X	X			X	X	X	X ^e	X	X	X		X	X

CONFIDENTIAL

204948

EDSS (Only MS patients)										X							
Investigational product																	
Treatment of antibiotic ^l		X										X					
Confirmation of day of re-treatment criteria ^l		X										X					
Treatment of investigational product ^k		X										X					
Confirmation of qualification for re-treatment criteria ^{j,l}					X ^{j,k}	X ^{j,k}	X ^{j,k}										
Concomitant meds / therapies	X	X	X	X	X	X	X	X	X	X	X	X	X	X	X	X	X

d = day (s)

- (a) Visit should not have occurred later than 48 weeks after 1st treatment. At 48 weeks after 1st treatment, study exit visit will be conducted.
- (b) Patient can request 2nd re-treatment at any time via telephone since week 12 after re-treatment. If the patient requests re-treatment via telephone, a qualification for re-treatment visit should be conducted within approximately 1-2 weeks of the patient request.
- (c) Bladder diary must have been completed for any 3 consecutive days in the week prior to the visit. The volume voided is recorded by subjects for one 24-hour period during the 3 day diary collection period.
- (d) Measured only body weight
- (e) Performed prior to treatment
- (f) These examination can be completed at the Qualification for re-treatment visit or at any time within 21 days prior to re-treatment
- (g) Urine culture and sensitivity is performed by the central laboratory when dipstick results are positive for nitrites or leukocyte esterase
- (h) For patients with doubtful reaction in urinary pregnancy test, the investigator (or subinvestigator) may conduct serum pregnancy test.
- (i) For patients without a UTI as determined from the urinalysis or urine culture and/or investigator opinion, prophylactic antibiotic are to be administered 1 to 3 days before study treatment, on the day of treatment, and 1 to 3 days after treatment. For patients with a UTI as determined from the urinalysis or urine culture and/or investigator opinion, an antibiotic to which the identified organism is sensitive is to be administered at least 5 days prior to study treatment and continued for at least 3 days following the procedure.
- (j) Patients who are not retreated will continue to visit at the scheduled study visit.
- (k) Re-treatment must be occurred after a minimum of 12 weeks (84 days) have elapsed since the previous treatment. Re-treatment should not have occurred later than 36 weeks after 1st treatment
- (l) If qualification for re-treatment criteria was met, the patient will undergo the exams specified in the column marked "If qualification for re-treatment criteria was met"

